6.1. Inclusion Criteria

Patients are eligible to be included in the study only if they meet all of the following criteria:

- [1] Have a histological diagnosis of advanced STS (by local pathology review), for which treatment with doxorubicin, ifosfamide and mesna is deemed appropriate by the investigator. Patients with a diagnosis of Grade 1 liposarcoma (atypical lipomatous neoplasms) are eligible if there is histological or radiographic evidence of evolution to more aggressive disease.
- [2] Have measurable or nonmeasurable but evaluable disease as defined by the Response Evaluation Criteria in Solid Tumors (RECIST 1.1) (Eisenhauer et al. 2009). Tumors within a previously irradiated field will be designated as “nontarget” lesions unless progression is documented or a biopsy is obtained to confirm persistence at least 90 days following completion of radiotherapy.
- [3] Are ≥ 18 years of age at the time of consent.
- [4] Have given written informed consent prior to any study-specific procedures.
- [5] Have adequate hematologic, organ and coagulation function within 2 weeks (14 days) prior to enrollment:
 - Absolute neutrophil count (ANC) $\geq 1.5 \times 10^9/L$. Granulocyte-colony-stimulating factor (G-CSF) cannot be administered within 2 weeks (14 days) prior to enrollment.
 - Platelet count $\geq 100 \times 10^9/L$
 - Hemoglobin $\geq 9.0 \text{ g/dL}$. No transfusions are allowed within 2 weeks (14 days) prior to enrollment.
 - Serum creatinine ≤ 1.5 times upper limit of normal (ULN). If creatinine is above the ULN, the patient’s creatinine clearance must be $\geq 65 \text{ mL/min}$ (refer to [Appendix 6](#) for the Cockcroft-Gault formula for creatinine clearance).
 - Total bilirubin within ULN (except for patients with Gilbert’s syndrome, who must have a total bilirubin $< 3 \text{ mg/dL}$)
 - Alanine aminotransferase (ALT)/aspartate aminotransferase (AST) $\leq 3.0 \times \text{ULN}$; if the liver has tumor involvement, AST and ALT $\leq 5.0 \times \text{ULN}$ are acceptable

- An adequate coagulation function as defined by international normalized ratio (INR) $\leq 1.5 \times$ ULN or prothrombin time $\leq 1.5 \times$ ULN, and partial thromboplastin time $\leq 1.5 \times$ ULN (unless receiving anticoagulant therapy). Patients receiving warfarin are recommended to switch to low molecular weight heparin and should have achieved stable coagulation status prior to the first dose of study treatment.

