7.4. Dosage Delays, Discontinuations and Modifications

To begin dosing at Cycle 2 and each Day 1 thereafter (for cycles in which olaratumab is administered with doxorubicin and ifosfamide), the following criteria must be fulfilled (see [Table JGDR.9](#) for hematological parameters for dosing olaratumab on Day 8):

- ANC $\geq 1.5 \times 10^3$ cells/ μ L (≥ 1500 cells/ μ L; $\geq 1.5 \times 10^9$ /L)
- Platelets $\geq 100 \times 10^3$ cells/ μ L ($\geq 100,000$ cells/ μ L; $\geq 100 \times 10^9$ cells/L)
- Hemoglobin ≥ 8.0 g/dL. Note: For study inclusion, hemoglobin ≥ 9.0 g/dL
- Total bilirubin below ULN. In patients with Gilbert's syndrome, total bilirubin should be <3 mg/dL
- Serum creatinine ≤ 1.5 times ULN. If creatinine is above ULN, the patient's creatinine clearance is ≥ 60 mL/min (refer to [Appendix 6](#) for the Cockcroft-Gault formula for creatinine clearance)
- AST and ALT $\leq 3 \times$ ULN, or $\leq 5 \times$ ULN if the transaminase elevation is due to liver metastases
- Nonhematologic toxicity must be Grade ≤ 2 or must have returned to baseline, unless the toxicity is deemed not clinically significant by the investigator or is a laboratory abnormality that is manageable by institutional standards (for example, low serum potassium, magnesium, or phosphate).

In addition, patients should be monitored for evidence of micro- and/or macroscopic hematuria and treated according to institutional standards.

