7.4.3.3. Ifosfamide Toxicities and Dose Modifications

Dose modifications of ifosfamide will follow the guidelines outlined below and may be adjusted according to local standard of care and label. Two reductions in ifosfamide dose for toxicity will be permitted during the study. If a third dose reduction is necessary, the patient will be discontinued from the combination therapy (olaratumab + doxorubicin/ifosfamide/mesna) and followed as outlined in Section 7.4.2.

General guidelines for ifosfamide dose modification are shown in Table JGDR.12. Dose modifications of ifosfamide due to hepatic impairment are shown in Table JGDR.13.

Table JGDR.12. General Guidelines for Dose Modification of Ifosfamide due to Toxicity

Worst Toxicity/Counts in Previous Cycle	Ifosfamide Dose Reduction ^a
Febrile neutropenia	First episode: Maintain full dose Subsequent episodes: Decrease 20%
Platelets <75,000/mm ³	If less than 1 week duration: Maintain full dose If greater than 1 week duration: Decrease 20%
Thrombocytopenic bleeding	Decrease 20%
Somnolence or other signs of encephalopathy	Discontinue combination therapy (olaratumab + doxorubicin/ifosfamide/mesna) and follow per Section 7.4.2. Administer methylene blue 50 mg intravenously every 4 hours until resolution.
Grade 3 or 4 neurotoxicity other than encephalopathy	Discontinue combination therapy (olaratumab + doxorubicin/ifosfamide/mesna) and follow per Section 7.4.2.
Grade 3 related organ toxicity/nonhematologic	Decrease 20%
Grade 4 related organ toxicity/nonhematologic	Discontinue combination therapy (olaratumab + doxorubicin/ifosfamide/mesna) and follow per Section 7.4.2.

Abbreviation: mg = milligrams.

^a Do not re-treat until criteria in Section 7.4 are met.

Table JGDR.13. Dose Modification of Ifosfamide due to Hepatic Impairment

Bilirubin	and/or	AST/ALT	Ifosfamide Dose Reduction ^a
1-2 × ULN		<2 × ULN	Full dose
2-4 × ULN		2-5 × ULN	75% of initial dose
>4 × ULN		>5 ULN	Discontinue combination therapy (olaratumab + doxorubicin/ifosfamide/mesna) and follow per Section 7.4.2.

Abbreviations: ALT = alanine aminotransferase; AST = aspartate aminotransferase; ULN = upper limit of normal.

^a Based on clinical judgment – less conservative adjustments can be considered if hepatic changes are secondary to metastases rather than hepatic cirrhosis or hepatitis.

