7.4.3.3.1. Ifosfamide-Associated Central Nervous System Toxicity

Central nervous system toxicity appears to be dose dependent, and is variable in onset, but usually resolves when ifosfamide is discontinued. Incidence is higher with higher doses, concomitant use of aprepitant, electrolyte imbalances, renal/hepatic impairment, or preexisting CNS disorders. It may manifest as transient mental status changes (somnolence, confusion, hallucination, disorientation and lethargy), cerebellar dysfunction, extrapyramidal symptoms, transient weakness, cranial nerve dysfunction, or seizure activity. Methylene blue, which may act as an electron acceptor or decrease chloroacetaldehyde formation, has been suggested as treatment or prophylaxis for ifosfamide-induced encephalopathy. Due to the potential for additive effects, drugs acting on the CNS (such as antiemetics, sedatives, narcotics, or antihistamines) must be used with particular caution or, if necessary, be discontinued in case of ifosfamide-induced encephalopathy.

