7.4.3.3.2. Ifosfamide-Associated Urotoxic Effects

The incidence of urotoxic effects without an uroprotector can be up to 40% and is dose dependent; coadministration of mesna and adequate hydration are mandatory in this study. Patients may present with hematuria, symptomatic cystitis, or bladder fibrosis. Past or concomitant radiation of the bladder or busulfan treatment may increase the risk of hemorrhagic cystitis. Several methods of treatment for established hematuria have been described: bladder irrigation with water or normal saline, intravesical instillation of astringents (alum, silver nitrate), systemic administration of antifibrinolitics (aminocaproic acid, tranexamic acid), cystoscopy to evacuate the bladder of clots, continuous bladder irrigation and intravesical prostaglandins. For severe or refractory hematuria, intravesical formalin, phenol, or prostaglandin has been used with or without surgical intervention (electrocautery, cryosurgery, diversion of urine flow, hypogastric artery ligation, or cystectomy). Discontinuation or dose reduction of ifosfamide should follow local standard of care and label for patients with macroscopic hematuria.

7.4.3.3.3. *Ifosfamide-Associated Proximal Tubular Damage*

Glomerular, proximal, or distal tubular impairment may all occur, often in combination and may progress even after ifosfamide has been discontinued. Proximal tubular damage often presents as Fanconi syndrome with low serum bicarbonate, proteinuria, glucosuria, aminoaciduria and hypochloremic metabolic acidosis. Risk factors for the development of nephrotoxicity include preexisting renal impairment, concurrent use of nephrotoxic drugs, reduced renal reserve (unilateral nephrectomy), hydronephrosis and total cumulative dose. Renal impairment may increase the risk of myelosuppression and possibly, cardiotoxicity. Mesna does not appear to be protective against the proximal tubular abnormalities induced by ifosfamide. Dose modifications guidelines of ifosfamide due to renal impairment are shown in [Table JGDR.14](#).

Table JGDR.14. Dose Modification of Ifosfamide due to Renal Impairment

Creatinine Clearance (mL/min) ^a	Ifosfamide Dose Reduction
>60	Full dose
40-60	Reduce to 75% of initial dose
20-40	Reduce to 50% of initial dose
<20	Discontinue combination therapy (olaratumab + doxorubicin/ifosfamide/mesna) and follow per Section 7.4.2 .

Abbreviations: min = minutes; mL = milliliters.

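### Creatinine clearance is checked at entry only when serum creatinine is above ULN, so a patient in the protocol's own reduced-dose range can be scheduled for full-dose ifosfamide in Cycle 1

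*Protocol*

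**What the plan says.** **Entry.** Protocol Section 6.1, criterion [5], caps serum creatinine at 1.5 times ULN. It adds a clearance requirement of at least 65 mL/min under one condition: "If creatinine is above the ULN". No other inclusion or exclusion criterion sets a clearance limit, and there is no upper age limit.

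**Start of later cycles.** The Section 7.4 list opens with "To begin dosing at Cycle 2 and each Day 1 thereafter", so it does not apply to Cycle 1. Its renal item has the same trigger, "If creatinine is above ULN, the patient's creatinine clearance is", with a limit of at least 60 mL/min.

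**Dose by renal function.** Table JGDR.14 (Section 7.4.3.3.3) is keyed to Cockcroft-Gault clearance, not to serum creatinine. It gives full dose above 60 mL/min. At 40-60 the instruction is "Reduce to 75% of initial dose"; at 20-40 it is 50%; below 20 the combination stops. Section 7.4.3.3 says that ifosfamide modifications "may be adjusted according to local standard of care and label".

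**Scheduled dose.** Section 5.1 and Table JGDR.6 give 10 g/m² of ifosfamide per cycle in the full-dose cohorts, which include the starting cohort. The reduced-ifosfamide cohorts receive 7.5 g/m².

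**The concern.** The entry gate is triggered by serum creatinine and the dose table by clearance, and the two can disagree. Creatinine within the normal range does not ensure clearance above 60 mL/min in older or lighter patients, particularly women. Such a patient passes criterion [5] with no clearance calculated and is not covered by Section 7.4 until Cycle 2.

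The protocol itself describes the risk. Section 7.4.3.3.3 states "Risk factors for the development of nephrotoxicity include preexisting renal impairment" and also "Renal impairment may increase the risk of myelosuppression and possibly, cardiotoxicity". On CNS toxicity, Section 7.4.3.3.1 states "Incidence is higher with higher doses, concomitant use of aprepitant, electrolyte imbalances, renal/hepatic impairment". Renal toxicity and encephalopathy are both adverse events of special interest (Section 9.2.3). What is at stake is patient safety in the first cycle, together with consistency between the entry rule and the dose table.

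**Working it through.** The plan gives no figure on this point to reproduce. The check applies the protocol's own formula.

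**Inputs from the documents.** The formula is in Appendix 6: clearance = (140 − age) × weight × f / (72 × creatinine in mg/dL), with f = 0.85 for women and 1.0 for men. The cut points are those of criterion [5], Section 7.4 and Table JGDR.14.

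**Input assumed.** The documents give no laboratory ULN for creatinine. I take 1.0 mg/dL for women and 1.2 mg/dL for men.

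**1. Example.** Woman aged 70, 60 kg, creatinine 0.9 mg/dL: (140 − 70) × 60 × 0.85 / (72 × 0.9) = 3570 / 64.8 = 55.1 mL/min. If 0.9 is within the local ULN, she passes criterion [5] without a clearance check, yet falls in the 75% row of Table JGDR.14.

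**2. Creatinine at which clearance falls to 60 mL/min.** Creatinine = (140 − age) × weight × f / (72 × 60).

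| | Age 60 | Age 70 | Age 75 |
|---|---|---|---|
| Woman, 60 kg | 0.94 | 0.83 | 0.77 |
| Man, 70 kg | 1.30 | 1.13 | 1.05 |

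**3. Age at which the gap opens under the assumed ULN.** Age = 140 − 4320 × ULN / (weight × f).
- Woman, 60 kg: 140 − 4320 × 1.0 / 51 = 55.3 years.
- Man, 70 kg: 140 − 4320 × 1.2 / 70 = 65.9 years.

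**4. Size of the dose discrepancy.** In a full-dose cohort, the 40-60 row gives 0.75 × 10 = 7.5 g/m². The scheduled 10 g/m² is 10 / 7.5 = 1.33 times that, a third more.

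**5. Share of patients, illustration only.** Every input to this simulation (2,000,000 draws) is assumed:
- half the patients women; ages 18 to 85;
- age normal with mean (SD) 55 (12), 60 (12) or 65 (10);
- weight 70 (14) kg for women and 82 (15) kg for men, limited to 40-150 kg;
- creatinine 0.75 (0.15) mg/dL for women and 0.95 (0.17) mg/dL for men, at least 0.4;
- ULN as above.

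Among patients with creatinine at or below ULN, the share with clearance of 60 mL/min or less is 4.7%, 6.9% and 9.4% for the three age settings. Changing one input at a time (mean weight by 5 kg, mean creatinine by 0.05, ULN by 0.1, or a weight-creatinine correlation of 0.3) gives 2.8% to 14.0%. Of those affected, 68% to 80% lie at 50-60 mL/min. Clearance below 40 occurs in 0.6% or less.

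**6. Rules side by side for Cycle 1, full-dose cohorts.**

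| Patient | Criterion [5] | Section 7.4 | Table JGDR.14, if applied |
|---|---|---|---|
| Creatinine above ULN, clearance 62 | Excluded | Not in force | Full dose |
| Creatinine normal, clearance 55 | Eligible, no check | Not in force | 75% |

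**The case against.** The strongest reply is that Table JGDR.14 already deals with this. It is keyed to clearance alone, its footnote names the Cockcroft-Gault formula, and it is not expressly confined to later cycles. Table JGDR.12, by contrast, is headed by events in the previous cycle. From Cycle 2, Section 7.4 bars Day 1 dosing when creatinine is raised and clearance is below 60. At those cycle starts, the rows below 60 can therefore operate only in patients with creatinine at or below ULN, which suggests that the authors expected clearance to be calculated in them.

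Much of this stands. A reader might infer that Cycle 1 has no renal dosing rule at all, and the text does not support that. What remains is ambiguity. The table sits among on-treatment modifications and reduces from an initial dose. Nothing says that it governs Cycle 1, and no entry or Cycle 1 start rule calls for the calculation when creatinine is normal.

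Other safeguards exist: investigator judgement of suitability (criteria [1] and [7]), local standard of care and the label, chemistry within 3 days before Day 1 and again on Days 8 and 15, and mandatory mesna and hydration. The label and local standards are not in the documents, so one cannot say that they are silent on renal function. They may catch some cases. Chemistry supplies a creatinine value but does not require a clearance, and Section 7.4.3.3.3 itself notes that mesna does not seem to protect the proximal tubule.

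A reader might also infer that extra toxicity in these patients would distort the DLT thresholds, since DLTs are counted in Cycle 1. The documents give neither the number of such patients nor their excess DLT risk, so that inference is not supported.

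**Conclusion.** The gap is real and modest. In the full-dose ifosfamide cohorts, the entry rule and the Cycle 2 start criteria together allow a patient with normal creatinine and clearance of 60 mL/min or less to be scheduled for 10 g/m² in Cycle 1. At 40-60 mL/min that is a third above what Table JGDR.14 would give. The gap's existence needs only the Appendix 6 formula and a creatinine value within the local normal range.

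Its frequency is not known. The 3% to 14% range rests wholly on assumed age, weight, creatinine and ULN values and does not model selection by performance status or investigator judgement. Under those inputs most affected patients lie at 50-60 mL/min, near the cut-off. The 10 g/m² figure does not apply to the reduced-ifosfamide cohorts. The point concerns patient safety and internal consistency; no DLT threshold, stated power or planned analysis changes.

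**What to change.** 1. Calculate and record the Appendix 6 clearance for every patient at screening and before each ifosfamide cycle, including Cycle 1, whatever the serum creatinine.
2. In criterion [5], apply one clearance threshold to all patients: either above 60 mL/min, which matches the full-dose row of Table JGDR.14, or the existing 65 mL/min. A single threshold avoids treating two patients at 62 mL/min differently because of their serum creatinine, and no one then starts Cycle 1 in a reduced-dose row.
3. In Section 7.4, state that from Cycle 2 Table JGDR.14 sets the ifosfamide dose for all patients, and how it fits with the 60 mL/min start criterion. As written, that criterion stops a patient with raised creatinine and clearance below 60, whereas the table would reduce the dose. A clearance of exactly 60 passes the criterion but falls in the 75% row.

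**Cost.** Age, sex, weight and creatinine are already collected, so the change is a few sentences and a derived eCRF field. The downside is that some patients with normal creatinine become ineligible. With a threshold above 60, the assumed inputs give a loss of 4.5% to 9.2% of currently eligible patients (2.7% to 13.7% over the range). Extra patients needed = n / (1 − loss) − n. For 45 patients at 4.5% this is 45 / 0.955 − 45 = 2.1; for 60 at 9.2% it is 60 / 0.908 − 60, about 6. Over the range it is about 1 to 10. Patients with raised creatinine and clearance above 60 but below 65 would become eligible and offset this slightly. A threshold of 65 for all would exclude more patients with normal creatinine; that share is not estimated here.

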6.2. Exclusion Criteria

Patients will be excluded from the study if they meet **any** of the following criteria:

- [15] Are currently enrolled in a clinical trial involving an investigational product or any other type of medical research judged not to be scientifically or medically compatible with this study.
- [16] Have participated within the past 30 days in a clinical trial involving an investigational product. If the previous investigational product has a long half-life, 3 months or 5 half-lives (whichever is longer) should have passed.
- [17] Have previously completed or withdrawn from any study investigating olaratumab.
- [18] Have received prior treatment with olaratumab, doxorubicin, or ifosfamide, or have participated in other trials investigating olaratumab.
- [19] Have received prior radiotherapy of the mediastinal/pericardial area or whole pelvis radiation.
- [20] Have known urinary outflow obstruction, or inflammation of the urinary bladder (cystitis).
- [21] Are diagnosed with gastrointestinal stromal tumor or Kaposi sarcoma.

[22] Have active central nervous system (CNS) or leptomeningeal metastasis (brain metastasis) at the time of enrollment. Patients with a history of CNS metastasis (previously treated with curative intent [for example, stereotactic radiation or surgery]) that has not progressed on follow-up imaging, have been asymptomatic for at least 60 days, and are not receiving systemic corticosteroids and/or anticonvulsants are eligible. Patients with signs or symptoms of neurological compromise should have appropriate radiographic imaging performed before enrollment to rule out brain metastasis.

[23] Have a history of another primary malignancy, with the exception of:

- curatively treated non-melanomatous skin cancer
- curatively treated cervical carcinoma in situ
- non-metastatic prostate cancer, or
- other primary nonhematologic malignancies treated with curative intent, no known active disease, and no treatment administered during the last 3 years prior to enrollment, that the investigator and Lilly Medical representative agree will not affect interpretation of study results or would be unsuitable for participation in the study.

[24] Have an active fungal, bacterial and/or known viral infection including human immunodeficiency virus or viral (A, B, or C) hepatitis (screening is not required).

[25] Have Grade 3 or 4 peripheral neuropathy per NCI-CTCAE Version 4.0.

[26] Have a serious cardiac condition, such as:

- unstable angina pectoris
- angioplasty, cardiac stenting or myocardial infarction within 6 months of enrollment
- valvulopathy that is severe, moderate, or deemed clinically significant
- arrhythmias that are symptomatic or require treatment

[27] Have a resting heart rate of >100 bpm.

[28] Have a QTcF interval of >450 msec for males and >470 msec for females on screening electrocardiogram (ECG) utilizing Fridericia's correction (refer to formula in [Appendix 7](#)).

[29] Have uncontrolled intercurrent illness including, but not limited to, an ongoing/active infection requiring parenteral antibiotics.

[30] Have a psychiatric illness/social situation that would limit compliance with study requirements.

- [31] Have electively planned or will require major surgery during the course of the study.
- [32] Are females who are pregnant or breastfeeding.

6.3. Screen Failures

The duration of the screening period is 14 days for the majority of procedures (see Section 2); certain noted procedures may be performed within 28 days of enrollment. Individuals who do not meet the criteria for participation in this study within the extended 28-day screening period (screen failure) may be re-screened after discussion with the Lilly CRP. Individuals may be re-screened a maximum of 1 time. The interval between re-screenings should be at least 28 days. If re-screening is performed, the individual must sign a new informed consent form (ICF) and will be assigned a new identification number.

Repeating laboratory tests during the 28-day screening period does not constitute re-screening. Screening laboratory tests may not be repeated more than once in order to meet eligibility during the 28-day screening period. If a repeat screening laboratory value meets eligibility, it is recommended that the test is rechecked to confirm stability.

7. Treatments

The investigator or his/her designee is responsible for the following:

- explaining the correct use of the drugs and planned duration of each individual's treatment to the patient and study site personnel
- verifying that instructions are followed properly
- maintaining accurate records of study drug dispensing and collection
- at the end of the study returning all unused medication to Lilly, or its designee, unless Lilly and sites have agreed all unused medications have to be destroyed by the site, as allowed by local law.

7.1. Treatment Administered (Dosing Schedule)

Table JGDR.6 shows the treatment regimens. On days where multiple study drugs are to be administered, the drugs should be administered in the order shown in Table JGDR.6.

Table JGDR.6. Treatments Administered (Dosing Schedule)

Phase and Dose Cohort		Drug Name and Dose	Day of 21-day (± 3 days) cycle	Total dose	Route and duration of administration	Notes
Dose-Finding Phase	Olara 15 mg/kg	Olaratumab 15 mg/kg ^a	D1 and D8		IV over 60 (± 5) min Infusion rate should not exceed 25 mg/min	See Section 7.1.1 for premedication requirements and Section 7.8.1 for IRR monitoring period requirements
		Doxorubicin 25 mg/m ² per day ^a	D1, D2, D3	75 mg/m ²	IV over less than 60 min or continuous IV infusion (according to institutional practice)	Administer after olara on D1 and after any required observation period
		Ifosfamide 2.5 g/m ² per day ^a	D1, D2, D3, D4 ^b	10 ^b g/m ²	IV over 3 hours (± 15 min)	Administer after dox on D1, D2, D3
		Mesna dose \geq 60% of ifos dose ^a	D1, D2, D3, D4 ^b		According to institutional practice	
	Olara Loading Dose Cycle	Olaratumab 20 mg/kg Cycle 1 Olaratumab 15 mg/kg Cycles 2 to 6 ^a	D1 and D8 D1 and D8		IV over 60 (± 5) min Infusion rate should not exceed 25 mg/min	See Section 7.1.1 for premedication requirements and Section 7.8.1 for IRR monitoring period requirements
		Doxorubicin 25 mg/m ² per day ^a	D1, D2, D3	75 mg/m ²	IV over less than 60 min or continuous IV infusion (according to institutional practice)	Administer after olara on D1 and after any required observation period
		Ifosfamide 2.5 g/m ² per day ^a	D1, D2, D3, D4 ^b	10 ^b g/m ²	IV over 3 hours (± 15 min)	Administer after dox on D1, D2, D3
		Mesna dose \geq 60% of ifos dose ^a	D1, D2, D3, D4 ^b		According to institutional practice	
Dose Confirmation Phase	Recommended Olara Dose	Olaratumab dose determined from Dose-Finding Phase ^a	D1 and D8		IV over 60 (± 5) min Infusion rate should not exceed 25 mg/min	See Section 7.1.1 for premedication requirements and Section 7.8.1 for IRR monitoring period requirements
		Doxorubicin 25 mg/m ² per day ^a	D1, D2, D3	75 mg/m ²	IV over less than 60 min or continuous IV infusion (according to institutional practice)	Administer after olara on D1 and after any required observation period
		Ifosfamide 2.5 g/m ² per day ^a	D1, D2, D3, D4 ^b	10 ^b g/m ²	IV over 3 hours (± 15 min)	Administer after dox on D1, D2, D3
		Mesna dose \geq 60% of ifos dose ^a	D1, D2, D3, D4 ^b		According to institutional practice	

Abbreviations: C = cycle; CRP = clinical research physician; D = day; DLT = dose-limiting toxicity; dox = doxorubicin; g = grams; ifos = ifosfamide; IRR= infusion-related reaction; IV = intravenous; kg = kilogram; m² = square meters; mg = milligrams; min = minutes; olara = olaratumab.

- a All patients will receive study therapy (olaratumab + doxorubicin/ifosfamide/mesna) for a maximum of 6 cycles, or until a discontinuation criterion is met. Patients who discontinue doxorubicin, ifosfamide and mesna treatment without evidence of disease progression will receive olaratumab as monotherapy until there is evidence of disease progression, death, intolerable toxicity, or other withdrawal criteria are met.
- b If DLT rules (see Section 7.2.2.1) are exceeded in the olaratumab 15-mg/kg cohort, a reduced dose of ifosfamide (7.5 g/m² total dose) will be explored. This reduced dose will be communicated by the Lilly CRP and will be accomplished by omitting the Day 4 dose (that is, ifosfamide will be administered at a dose of 2.5 g/m² on D1, D2 and D3). The Day 4 dose of mesna will be correspondingly omitted. A Loading Dose Cycle of olaratumab (20 mg/kg on Days 1 and 8 of C1, then 15 mg/kg on Days 1 and 8 of subsequent cycles) may also be explored in combination with the reduced dose of ifosfamide.

